9.1 Overview

The study will be co-ordinated from the Institute of Metabolic Science, Addenbrooke's Hospital, Cambridge, and performed at following sites:

1. Addenbrooke's Hospital, Cambridge, UK
2. Royal Hospital for Sick Children, Edinburgh, UK
3. Leeds Teaching Hospital, Leeds, UK
4. Manchester Royal Infirmary, Manchester, UK
5. International Diabetes Center at Park Nicollet, Minneapolis, USA
6. Barbara Davis Center for Childhood Diabetes, Aurora, USA

After recruitment, consent, and run-in period, subjects will be randomised for three months home use of real-time CGM combined with automated day and night closed loop insulin delivery or three months during which they will use sensor augmented pump therapy alone.

The study includes up to 11 visits and 6 telephone/email contacts for subjects completing the study. The visit to set up automated closed loop for the first time may take place in the home setting or alternatively in an in-patient facility. All other visits can take place at the hospital clinic, home or other suitable meeting place, according to participants' convenience. Maximum time in study is 18 weeks.

Table 1 outlines study activities when participant is randomised to day and night closed loop (intervention group).

Table 2 outlines study activities when participant is randomised to sensor augmented pump therapy alone (control group).

Table 1. Schedule of study visits / phone contacts when the participant is randomised to day and night closed loop combined with pump suspend feature (intervention group).

	Visit/ contact	Description	Start relative to previous / next Visit / Activity	Duration
	Visit 1	Recruitment visit: Consent, HbA1c, screening bloods & questionnaires, urine pregnancy test	-	1-4 hours
Training & Run-in (4 wks)	Visit 2	Insulin pump training and the initiation study pump Competency assessment	Within 1 to 3 weeks of Visit 1	3-4 hours
	Visit 3	CGM training Initiation of CGM Weekly contact via phone/email Competency assessment	Within 3 to 7 days of Visit 2	2-3 hours
	*Visit 4	Review pump and CGM data & optimisation of treatment & compliance assessment & randomisation	After 4 weeks of Visit 3	<1 hour
	Contact	Qualitative interview (with a subset of participants/family members)	After randomisation but before Visit 5	<1 hour
CL + LGS Intervention (3 months)	Visit 5	CL initiation at clinic/home - urine pregnancy test - CL and suspend feature training - competency assessment - HbA1c	Within 1 week of Visit 3	2-6 hours

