9.2 Recruitment Visit and Screening Assessment (Visit 1)

Once the subjects have agreed to participate in the study, they will be invited for the recruitment visit, when the following activities will be performed by the research team:

- written informed consent/assent
- checking inclusion and exclusion criteria
- medical (diabetes) history
- body weight and height measurement; calculation of BMI
- record of current insulin therapy
- urine pregnancy test (females of child-bearing potential)
- record of occupation and educational attainment

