9.5.1 Compliance Assessment

During Visit 4, participant's compliance of using the study CGM and study pump over preceding 14 days will be assessed. To proceed with the study subject needs to demonstrate correct use of study insulin pump including use of bolus calculator over 75% of meal boluses and at least 12 days' worth of CGM data during last 14 days of run-in period. In addition, subject should carry out upload of CGM and pump data at weekly intervals. If subject fails to demonstrate compliance, the study will be terminated and subject will be removed from the study.

Subject randomisation for the treatment intervention will take place during the week following Visit 4. Maximum period allowed between Visit 3 and Visits 5 is six weeks with a minimum of four weeks.

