9.7 Baseline Qualitative Interview

A subset of subjects/guardians randomised to the use of day and night closed loop with pump suspend feature will be invited for a qualitative interview (face to face or telephone interview) at a mutually convenient time, see section 12.2.2. Whenever possible, the interview will occur before Visit 8.

9.8 Visit 5 (Initiation of Study Treatment; within 1 Week of Visit 4 and at least 4 Weeks after Visit 3)

Subject will arrive at the clinical facility at the agreed time. Urine pregnancy test will be performed on arrival for all females of child bearing age and all subjects will have a blood test for HbA1c. Body weight measurement will be made. Subjects will be provided with necessary training on use of study devices according to randomisation. Competency assessment will be made. During the three months home treatment period, the subject will be asked to upload the study insulin pump and CGM at weekly intervals.

During the three months home closed loop treatment, the subject is allowed to drive while adhering to usual precautions and country specific rules and regulations.

During the first 2 weeks of each study period subject will be advised against international travel. During the rest of the study period, participants are allowed to travel internationally according to guidelines provided in the participant information sheet.

Subjects will be provided with 24 hour telephone helpline and will also be given written instructions about dealing with low and high glucose at home and when to contact study team. It is also possible to conduct Visit 8 in subject's home.

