10.2 Secondary Endpoints

Secondary endpoints include:

- HbA1c at 12 weeks
- Time spent below target glucose (3.9mmol/l) (70mg/dl)
- Time spent above target glucose (10.0 mmol/l) (180 mg/dl)
- Average, standard deviation, and coefficient of variation of glucose levels
- The time with glucose levels < 3.5 mmol/l (63mg/dl) and <2.8 mmol/l (50mg/dl)
- The time with glucose levels in the significant hyperglycaemia (glucose levels > 16.7 mmol/l) (300mg/dl)
- Total, basal and bolus insulin dose
- AUC of glucose below 3.5mmol/l (63mg/dl)
- Number of pump suspend events (applicable to intervention arm)
- Change in body weight from screening to end of study

Glucose endpoints will be based on sensor glucose.

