12.1 Procedures

12.1.1 Height and Weight

These will be recorded at the study initiation visit at screening. Weight will be also measured at the start and the end the study interventions. Height will be measured in centimetres using a calibrated stadiometer. Weight will be measured in kilograms using a calibrated electronic scale.

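### The weight-change endpoint starts at screening although weight is measured again when study treatment starts, so roughly a third of its interval, and up to 45% on the widest visit windows, precedes treatment

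*Protocol*

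**What the plan says.** The synopsis and section 10.2 of the protocol give the same definition: "Change in body weight from screening to end of study". Section 14.2 places this outcome among six selected secondary outcomes judged at p<0.05. The others are HbA1c, glucose CV, time below 3.9 mmol/l, time above 10.0 mmol/l and total daily insulin.

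Weight is recorded three times:

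- At Visit 1, section 9.2 lists "body weight and height measurement; calculation of BMI".
- At Visit 5, when study treatment starts, section 9.8 states "Body weight measurement will be made".
- At Visit 11, section 9.14 asks for weight again.

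Section 12.1.1 confirms the last two: "Weight will be also measured at the start and the end the study interventions". Nothing in the protocol gives the Visit 5 weight a role in this endpoint.

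**The concern.** The question for this outcome is what 12 weeks of closed loop does to weight compared with sensor-augmented pump therapy. Starting at Visit 1 adds the wait for pump training, the move to the study pump, the start of CGM in people who were not regular users, and a run-in of at least four weeks during which downloaded data may be used to optimise treatment. Both arms go through all of this, and none of it is the randomised contrast.

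Weight change in that lead-in adds spread to the outcome and carries no information on the treatment effect. Half of the planned sample is aged 6 to 21, so growth contributes too, over a lead-in whose length differs between participants. Precision on a formally tested outcome is at stake, as is the meaning of the within-arm changes.

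**Working it through.** **Inputs (protocol)**

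- Visit 1 to Visit 2: "Within 1 to 3 weeks of Visit 1" (Tables 1 and 2), so 7 to 21 days.
- Visit 2 to Visit 3: "Within 3 to 7 days of Visit 2" (Tables 1 and 2), so 3 to 7 days.
- Visit 3 to Visit 5: "Maximum period allowed between Visit 3 and Visits 5 is six weeks with a minimum of four weeks" (section 9.5.1), so 28 to 42 days.
- Visit 5 to Visit 11: 7 + 7 + 14 + 28 + 28 = 84 days (Tables 1 and 2), which agrees with 12 weeks of treatment.
- Maximum time in study: 18 weeks (synopsis and section 9.1).

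Table 1 times Visit 5 from Visit 3, with a one-week limit. That conflicts with Table 2 and with sections 9.5.1 and 9.8, so it was not used.

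**The stated 18 weeks.** Counted from Visit 3, 6 + 12 = 18 weeks, an exact match. Counted from Visit 1, the windows give 17.4 to 22.0 weeks. The protocol does not say where the 18 weeks start, so both readings are carried.

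**Share of the interval before treatment** = pre-treatment days / (pre-treatment days + 84)

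| Path | Pre-treatment days | Total days | Share |
|---|---|---|---|
| Shortest windows | 7 + 3 + 28 = 38 | 122 (17.4 weeks) | 31.1% |
| 18-week limit from Visit 1 | 126 − 84 = 42 | 126 (18 weeks) | 33.3% |
| Visit 4 at exactly 4 weeks, Visit 5 a week later, other windows at their longest | 21 + 7 + 35 = 63 | 147 (21 weeks) | 42.9% |
| Longest windows | 21 + 7 + 42 = 70 | 154 (22 weeks) | 45.5% |

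The third path follows section 9.8, which puts Visit 5 "within 1 Week of Visit 4 and at least 4 Weeks after Visit 3". The lead-in can differ between participants by up to 70 − 38 = 32 days.

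**Effect on precision (illustration).** The protocol gives no SD for weight or weight change. Assume that the variance of the change is proportional to elapsed time. The variance ratio against a Visit 5 baseline is then (pre-treatment days + 84) / 84, and the confidence interval widens by its square root:

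- Shortest windows: 122/84 = 1.45; interval 21% wider.
- 18-week limit from Visit 1: 126/84 = 1.50; interval 22% wider.
- Longest windows: 154/84 = 1.83; interval 35% wider.

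Part of the variance, such as scale error, clothing and hydration, does not depend on time and enters both versions of the endpoint equally. If that part were as large as the 84-day drift variance (again an assumption), the ratios would fall to (84 + 122)/168 = 1.23, (84 + 126)/168 = 1.25 and (84 + 154)/168 = 1.42. If it dominated, they would approach 1.

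**With a Visit 5 baseline** the interval is 84 days and none of it precedes treatment.

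**The case against.** The best defence is that screening is a legitimate baseline. It is strictly before randomisation, whereas Visit 5 can fall up to about a week after it in an open-label trial. The synopsis and section 10.2 agree with each other. Screening also serves as baseline elsewhere: the quality-of-life questionnaires are taken only at screening and at the end (sections 12.2.1 and 14.7). The HbA1c endpoint in section 10.2 names no baseline, so it sets no rule that weight breaks. The model covariates may be settled in a separate analysis plan that is not at hand.

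Most of this stands, and it limits the point. A reader might infer that the treatment comparison is biased. The protocol does not support that: the lead-in change comes before randomisation, or within about a week after it and before study treatment, so it is expected to be equal in the two arms. A reader might also take nearly half as the settled share. That needs the widest windows, whose 22-week total exceeds the stated 18 weeks unless those are counted from Visit 3.

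The defence does not remove the efficiency argument. Adjusting for screening weight cannot take out change that occurs after screening, and the start point is fixed in the endpoint wording itself, not left to an analysis plan.

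**Conclusion.** This is a cheap improvement, not an error or an internal contradiction in the endpoint definition. The part of the interval before treatment is 31% to 45% by the visit windows, or 31% to 33% if the 18-week maximum is counted from Visit 1. The between-arm comparison remains valid. The cost is lower precision, and within-arm changes that combine run-in effects, and growth in the younger half, with treatment.

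The shares rest only on the protocol's own windows. The variance figures, about 45% to 50% under the 18-week limit and up to 83% at the widest, rest on an assumed drift model and are upper-end illustrations. The actual loss cannot be calculated from the protocol.

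**What to change.** In the synopsis and section 10.2, redefine the endpoint as change in body weight from Visit 5 (start of study treatment) to Visit 11. State that the model adjusts for Visit 5 weight, and tabulate screening weight descriptively.

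The cost is wording only, because the Visit 5 weight is already collected. The one drawback is that Visit 5 may be up to about a week after open-label randomisation, though still before study treatment. A sensitivity analysis with screening weight as the baseline covers it.

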10.3 Safety Evaluation

Safety evaluation will comprise number of episodes of severe hypoglycaemia as well as the number of subjects experiencing severe hypoglycaemia, severe hyperglycaemia (fingerprick glucose >16.7 mmol/l) (>300mg/dl) and plasma ketones >0.6mmol/l), diabetic ketoacidosis, and other adverse events. Subjects will be asked to measure blood or urine ketone levels on waking in the morning if their finger prick glucose is above 14mmol/l (250mg/dl), as part of the safety evaluation for hyperglycaemia.

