Procedures for safety monitoring during trial	
Standard operating procedures for monitoring and reporting of all adverse events will be in place, including serious adverse events (SAE), serious adverse device effects (SADE) and specific adverse events (AE) such as severe hypoglycaemia.
 
Subjects will be asked to test and record blood or urine ketones if their finger prick glucose is above 14.0mmol/l (250mg/dl) in the morning on waking, as part of the safety assessment for hyperglycaemia.
 
A data safety and monitoring board (DSMB) will be informed of all serious adverse events and any unanticipated serious adverse device effects that occur during the study and will review compiled adverse event data at periodic intervals.

Criteria for withdrawal of patients on safety grounds

A subject, parent, or guardian may terminate participation in the study at any time without necessarily giving a reason and without any personal disadvantage. An investigator can stop the participation of a subject after consideration of the benefit/risk ratio. Possible reasons are:

1. Serious adverse events
2. Significant protocol violation or non-compliance
3. Failure to satisfy competency assessment
4. Decision by the investigator, or the sponsor, that termination is in the subject's best medical interest
5. Pregnancy, planned pregnancy, or breast feeding
6. Allergic reaction to insulin
7. Technical grounds (e.g. subject relocates)

3 Summary

The main study objective is to determine whether day and night automated closed loop glucose control combined with pump suspend feature will improve glucose control and reduce the burden of hypoglycaemia compared to sensor augmented insulin pump therapy alone.

This is an open-label, multi-centre, multi-national, single-period, randomised, parallel group design study, involving a three-month period of home study during which day and night glucose levels will be controlled either by a closed loop system combined with pump suspend feature (intervention group) or by sensor augmented insulin pump therapy (control group).

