9.18 Subject reimbursement

The study will provide the CGM device, insulin pump, closed loop components, related consumables, and glucose test strips. A study fee will be paid to reflect local practice. The amount

paid will be specified in the participant information sheet and REC/IRB application form. Reasonable travel expenses will also be reimbursed. After completing the study, subjects will not keep the study devices. They will revert to their conventional insulin pump therapy.

10 Endpoints

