11.2.4 Hyperglycaemia, Ketonemia and Diabetic Ketoacidosis

Diabetic Ketoacidosis (DKA) is defined as: hyperglycemia (blood glucose >250 mg/dl or >13.9 mmol/l) with either low serum bicarbonate (<15 mEq/l) and/or low pH (<7.24), anion gap (> 12) and either ketonemia or ketonuria and requiring treatment within a health-care facility (American Diabetes Association Workgroup on Hypoglycemia, Diabetes Care 28:1245-1249, 2005).

DKA will be regarded as a foreseeable serious adverse event and a severe adverse event form will be completed.

Severe hyperglycaemic events (fingerprick glucose >300 mg/dl/16.7mmol/l and blood ketones >0.6mmol/l) will be recorded as Adverse Events. Non-severe hyperglycaemia events will not be reported or considered as adverse events.

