14.3 Safety Analysis

Below safety outcomes will be tabulated by treatment group:

- Number of subjects with any diabetic ketoacidosis events
- Number of episodes of diabetic ketoacidosis events per subject and incidence rate per 100-person years
- Number of subjects with any severe hypoglycaemia events
- Number of episodes of severe hypoglycaemia events per subject and incidence rate per 100-person years
- Number of subjects with any severe hyperglycaemia events as defined by fingerprick glucose >16.7 mmol/l (>300 mg/dl) and plasma ketones >0.6 mmol/l
- Number of episodes of severe hyperglycaemia events per subject and incidence rate per 100-person years

Above safety data will be tabulated for all subjects in the two intervention periods, including drop-outs and withdrawals, irrespective of whether CGM data are available and irrespective of whether closed loop was operational. All adverse events will be listed for the entire study duration.

If there are enough observed events to allow formal statistical modelling for above safety outcomes, the following analyses will be conducted. The event rates will be compared using a Poisson regression model adjusting for random site effect. If outliers exist, a robust Poisson regression model will be used instead. Binary variables will be compared using a logistic regression model

adjusting for random site effect. Models involve severe hypoglycaemia events will also adjust for severe hypoglycaemia in the previous 6 months before enrolment.

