14.9 Statistical Methods

The respective values obtained during the 12-week randomised interventions contrasting the closed loop combined with pump suspend feature against the sensor augmented pump therapy will be compared using independent samples statistical techniques. For non-normally distributed parameters transformation or nonparametric analyses will be used.

Primary analysis will be a single comparison and no attempt will be formally made to control the overall type I error rate for the secondary outcomes. A 5% significance level will be used to declare statistical significance for the primary comparison.

Severe hypoglycaemic events and ketone-positive hyperglycaemia will be tabulated in each treatment group, which will be compared using repeated measures logistic regression (generalised estimator equation).

Safety data including severe hypoglycaemia events and ketone-positive hyperglycaemia will be tabulated for all subjects, including drop-outs and withdrawals, irrespective of whether CGM data are available and irrespective of whether closed loop was operational.

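### Severe hyperglycaemia is defined by a blood or plasma ketone value at any hour, but the only ketone test explicitly requested is on waking and may be on urine

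*Protocol*

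**What the plan says.** **The outcome.** Section 10.3 lists as a safety outcome "severe hyperglycaemia (fingerprick glucose >16.7 mmol/l) (>300mg/dl) and plasma ketones >0.6mmol/l". Section 11.2.4 repeats the definition for adverse-event recording: "Severe hyperglycaemic events (fingerprick glucose >300 mg/dl/16.7mmol/l and blood ketones >0.6mmol/l) will be recorded as Adverse Events". Neither places a time-of-day limit on the event.

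**The analysis.** Section 14.3 tabulates the number of subjects affected and also "Number of episodes of severe hyperglycaemia events per subject and incidence rate per 100-person years". If there are enough events, it adds Poisson and logistic models. Section 14.9 plans a comparison as well: "Severe hypoglycaemic events and ketone-positive hyperglycaemia will be tabulated in each treatment group, which will be compared using repeated measures logistic regression".

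**The measurement.** Section 10.3 asks subjects to "measure blood or urine ketone levels on waking in the morning if their finger prick glucose is above 14mmol/l" and calls this part of the safety evaluation for hyperglycaemia. The synopsis, under procedures for safety monitoring, says the same: subjects are to "test and record blood or urine ketones if their finger prick glucose is above 14.0mmol/l (250mg/dl) in the morning on waking". The protocol contains no other explicit request for a ketone test.

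**What is not recorded.** Section 11.1.2 removes hyperglycaemia without ketonaemia above 0.6 mmol/l from adverse-event recording. Section 11.2.4 does the same for hyperglycaemia that is not severe.

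**The concern.** The stated way of measuring ketones does not produce what the outcome definition needs. A participant who follows the instruction exactly, using a urine test, gives a result that cannot be placed above or below 0.6 mmol/l in blood. An episode at another hour has no requested test. In both cases the episode drops out of adverse-event recording, and nothing separates an untested episode from one that was tested and negative.

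Severe hyperglycaemia is one of three event types in the formal safety analysis, with severe hypoglycaemia and ketoacidosis. The intervention runs day and night and can suspend insulin automatically. Section 4.3 cites rebound hyperglycaemia and ketosis as things that earlier suspension studies looked for and did not find. Section 4.11 says that no study had yet combined suspension with closed loop. A rate per 100 person-years will be read as covering all hours, and a low rate could reflect few events or few usable tests. No later analysis can recover a blood ketone value that was never measured.

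**Working it through.** The protocol gives no figure for ascertainment, so there is none to reproduce. The check is a comparison of passages, then a test of whether the undercount can be sized.

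**1. Definition against requested test**

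| Element | Outcome (10.3, 11.2.4, 14.3) | Requested test (synopsis, 10.3) | Match? |
|---|---|---|---|
| Glucose | fingerprick above 16.7 mmol/l | fingerprick above 14 mmol/l | Yes: the trigger is lower, so it covers the criterion |
| Specimen | plasma or blood, in mmol/l | blood or urine | No |
| Timing | any time | on waking | No |

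The units agree: 14 × 18.016 = 252 mg/dl and 16.7 × 18.016 = 301 mg/dl, against the stated 250 and 300. The mismatch lies only in specimen and timing.

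**2. Is there a rule for urine results?** None is stated. In the same section 11.2.4, the ketoacidosis definition accepts ketones in blood or in urine. The severe-hyperglycaemia definition asks for blood only.

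**3. Can the undercount be sized?** Let

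- w = share of qualifying episodes present at the waking check
- b = share of ketone tests done on blood
- s = share of non-waking episodes tested anyway, for example under sick-day advice

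The captured share is b × [w + (1 − w) × s], taking b to be the same at all hours. The protocol gives none of the three inputs, so every value below is an assumption.

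| w | b | s | Captured share |
|---|---|---|---|
| 0.10 | 0.5 | 0 | 0.5 × 0.10 = 5% |
| 0.25 | 0.8 | 0.5 | 0.8 × (0.25 + 0.75 × 0.5) = 50% |
| 0.50 | 1 | 0 | 1 × 0.50 = 50% |
| 0.75 | 1 | 0.8 | 0.75 + 0.25 × 0.8 = 95% |

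With blood tests only and no testing outside waking, the captured share equals w. More than half of episodes would then be missed only if fewer than half were present at waking.

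**4. What one missed episode does to the rate.** Assume 84 subjects split equally and followed in full for 84 days. Exposure per arm is 42 × 84 / 365 = 9.7 person-years. One uncounted episode lowers that arm's rate by 100 / 9.7, or about 10 per 100 person-years.

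**The case against.** **Testing at other times is not excluded.** The waking test is a request, not a limit, and a blood value obtained at any hour counts under section 11.2.4. Other routes exist: training on sick-day rules and hyperglycaemia (9.3), written advice on high glucose (9.8), a 24-hour helpline (9.17) and adverse-event questioning at each visit (11.2.2). This stands, and it rules out saying that non-waking episodes cannot be counted. It does not settle the point. The content of the training and written advice is not in the protocol, none of it is linked to this outcome, and questioning at a visit cannot supply a ketone value that was never taken.

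**Other outcomes capture hyperglycaemia.** Sensor time above 16.7 mmol/l is a secondary endpoint (10.2). Ketoacidosis is counted at any hour, with blood or urine ketones (11.2.4, 14.3). This also stands: an untested episode is not invisible. But sensor time carries no ketone information, and ketoacidosis is a graver event.

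**Stronger readings that the protocol does not support**

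- A reader might infer that most episodes are missed. Taking one waking reading out of the four daily fingerpricks in inclusion criterion 5, and losing an assumed 25% to 75% of tests to urine, gives 0.25 × 0.75 = 19% down to 0.25 × 0.25 = 6% captured. That needs an even spread of episodes over the readings, no testing at other times and a urine share with no source. Four is also only the minimum number of readings.
- A reader might infer bias in favour of closed loop, because the earlier studies in sections 4.5 to 4.8 were overnight. The day-and-night study in section 4.9 reports more time in target both by day (p=0.017) and by night (p=0.013). The testing request is also the same in both arms. Bias would need the arms to differ in how often they test or in the share of episodes seen at waking. That is possible in an open-label trial but is not shown.
- A reader might infer from section 9.18 that no ketone strips are supplied: "The study will provide the CGM device, insulin pump, closed loop components, related consumables, and glucose test strips". That is a reimbursement paragraph, and related consumables are on its list.

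**Conclusion.** The point holds as a mismatch between an outcome definition and its stated measurement. The outcome needs a blood or plasma ketone value and has no time limit. The only explicit test request is on waking and accepts urine. The instruction, followed exactly, can yield results that cannot be classified, and episodes without a qualifying value are left out of adverse-event recording.

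The count and the rate may be too low. The amount cannot be estimated from the protocol, because it gives neither the timing of episodes, nor the split between blood and urine tests, nor the rate of testing outside waking. The 5% to 95% range shows only how far the answer depends on those inputs. With about 10 person-years per arm, even a few missed episodes would change the reported rate visibly. No direction of bias between arms is established. The primary analysis is unaffected. This should be corrected, since it concerns a formal safety outcome and the remedy is cheap.

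**What to change.** Reconcile the synopsis and sections 10.3, 11.1.2, 11.2.4 and 14.3 so that the specimen and timing of the ketone measurement match the outcome definition. Which testing rule applies is for the clinical team.

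Whichever rule is kept:

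- record the time and specimen of each ketone test on the CRF, in both arms
- tabulate urine-positive episodes above the glucose threshold in a separate category, stated in advance
- report the number of ketone tests per arm beside the event counts
- do not present the rate as full 24-hour ascertainment unless the testing supports it. A label restricted to waking events would be accurate only if the count is in fact limited to waking tests.

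The cost is protocol and CRF wording, a little more data entry and tabulation, and possibly a slightly higher event count. If the clinical team changes the testing itself, the cost of supplies follows from that decision.
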